**6.3.13.10 Adherence**

Adherence will be calculated in two ways as follows:

- Dose adherence: dose administered as registered in diary / doses prescribed
- Frequency adherence: number of days with infusions as registered in the diary / number of days on which infusion was prescribed

Dose prescribed will be taken from the CRF. The frequency as entered in the CRF will also be used for the calculation of number of days on which dose was prescribed.

The number of doses administered will be calculated from the data entered into the eDiary and the eCRF.

This calculation will be done for each period, and the results will be listed and summarized descriptively using the respective period specific analysis set. For the calculation of dose adherence also see also Section 6.3.14 on the handling of doses recorded in duplicate (entered in both subject diary and CRF).

**6.3.14 Exposure**

All doses of rFVIIIFc will be listed using the ITIFAS, including date, time, purpose of dose, total dose, number of vials and kit numbers. A similar listing will be produced for bypass agents, including date, time, product, purpose of dose and amount of dose. Both doses given on-site and recorded in the patient diary will be included.

## PAREXEL International

### Statistical Analysis Plan

A summary table will be presented, showing descriptive statistics for the duration of exposure (date of last treatment – date of first treatment) and the total number of exposure days (sum of days with exposure).

In addition, all treatment regimens (including the derived first) will be listed for each patient including start date, stop date, dose (IU/kg), dosing interval and reason for regimen change. There will be an additional listing, including only treatments regimens during the follow-up period, using the FUFAS.

A figure will present weekly dose amount (IU/kg) versus time by patient (spaghetti plot) for the tapering period using the TPFAS analysis set.

Each dose should be entered only in the eCRF OR in the patient diary, but it is possible that it is entered in both by mistake. In this case, an attempt will be made to identify and flag duplicated dosing entries, as follows: two doses are considered duplicates, when:

- they were received by the same patient,
- the dose levels match,
- one dose is from the subject diary, the other is from the CRF, and
- the two recorded doses took place within 2 hours of each other. This is considered sufficient to not mistakenly flag morning & evening doses on a twice daily regimen as duplicates but allows for inaccuracy in entering the exact time in the diary by the patient.

In case of duplicates, the record from the subject diary will be flagged. Flagged dosing entries will be excluded from summary statistics.

Any modifications to this identification procedure for duplicated dosing entries will be described in detail in the CSR.

#### **6.3.15 Safety and Tolerability Analysis**

The analysis of the safety variables will be based on the ITIFAS set.

##### **6.3.15.1 Adverse Events**

All AEs will be listed including the items mentioned in Section 6.1.6.1 (except whether autopsy was performed). Additional listings will be produced for the following:

- Serious AEs
- Serious AEs leading to death

**PAREXEL International**  
**Statistical Analysis Plan**

- AEs leading to discontinuation

In addition, the following summaries will be presented:

- Overall summary, displaying the number of:
  - TEAEs (overall, regardless of seriousness)
  - Serious AEs
  - Serious TEAEs
  - Non serious TEAEs
  - Related TEAEs
  - Severity of AEs
  - AEs leading to discontinuation
  - AEs leading to death
- TEAEs by SOC and PT
- Serious AEs by Severity, SOC and PT (including pre-treatment SAEs shown as a separate period)
- Non-serious TEAEs by Severity, SOC and PT
- Non-serious TEAEs by Relationship, SOC and PT
- Serious TEAEs by Relationship, SOC and PT

The overall summary and the summary of TEAEs by SOC and PT will display AEs by period using columns for the different periods. All other AE summaries will also be by period but will be split into multiple parts by period.

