## **7 Investigational plan**

### **7.1 Overall study design and plan**

This is an open-label, single-arm, interventional multi-center study designed to explore ITI treatment performed with rFVIIIFc within a timeframe of 60 weeks in patients with severe haemophilia A, who have failed previous attempts at tolerization including use of immunosuppressants.

The patient must have undergone at least one failed ITI treatment attempt with the following characteristics:

- A minimum FVIII dose equivalent to the low dose arm of the International ITI study (50 IU/kg, 3 times/week)
- A minimum ITI treatment period of 33 months or

[figure not shown]
- Shorter than 33 months if no downward trend of at least 20% in the inhibitor titer in any 6-month period after the initial 3 months of the ITI treatment indicating a stagnation in the tolerization attempt

The use of immunosuppressant drugs without the combination of the above is not sufficient.

The study will be conducted in 20 patients, receiving at least one dose, recruited from countries in Europe and in North America. The study consists of a 4 to 6 week screening period, a maximum 60 week ITI period, a 16 week tapering period and a 32 week follow-up period. Only patients who achieve ITI success will enter the tapering and follow-up periods.

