**Figure 1**

**Study flow chart**

\* Only patients who achieve ITI success within 60 weeks

The duration of individual patient study participation will vary based on time to ITI success.

The maximum individual patient study duration is expected to be approximately 116 weeks, i.e., 6 weeks of screening + 60 weeks of treatment +16 weeks of tapering + 32 weeks of follow-up + an additional 2 weeks for safety follow-up.

The minimum individual patient study duration is expected to be approximately 42 weeks, i.e., 4 weeks of screening + 36 weeks of ITI treatment + an additional 2 weeks for safety follow-up.

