#### **7.1.4 Follow-up period**

After completion of the tapering period, patients will enter the follow-up period. During the follow-up period patients will be treated prophylactically for up to 32 weeks with dose and frequency prescribed by the investigator, and according to the label and clinical response of the patient. If the tapering period has been prolonged, the follow-up period should be shortened accordingly but should not be less than 24 weeks.

During the follow-up period patients will visit the clinic every 12 weeks and undergo procedures and assessments as per the schedule of events (Table 2). At each visit, samples for inhibitor titer and IR assessments will be drawn to monitor for relapse. A patient with confirmed relapse criteria will complete the end of treatment visit.

In order to avoid bleeds and a relapse of the inhibitor titer, FVIII:C levels should be kept  $\geq 1$  IU/dL. Bleeding episodes during the follow-up period should be treated with rFVIIIFc, with doses according to investigator judgment and local practice. In specific situations, e.g. if bleeding is unresponsive to treatment with rFVIIIFc, treatment with bypassing agents may be considered as judged by the investigator. Such use is to be notified to the medical monitor and the rational documented in the medical records. Patients with bleedings during the follow-up period is to be tested for recurrence of inhibitors.

At the end of treatment visit, pharmacokinetic assessments to determine IR and half-life, if deemed measurable based on pre-dose FVIII:C, will be performed. Patients are required to have at least a 24-hour washout period prior to the half-life assessment.

Throughout the follow-up period rFVIIIFc administration and any bleeding episodes will be registered by the patient and/or his caregiver in a study-specific diary. The diary data will be reviewed by the investigator on an ongoing basis and discussed with the patient at each visit.

After the patient has completed the end of treatment visit, they should be treated and followed-up according to investigator judgment and local practice. No further investigational medicinal product will be provided.

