c Vital signs include blood pressure, pulse rate, respiratory rate, and temperature. Postdose assessments following injections should be taken approximately 20 minutes after the end of the rFVIIIFc injection.

d During the tapering period, samples should be drawn every 12th week for testing.

e Patients will be instructed that they will receive their daily dose of rFVIIIFc during the study visit after the samples for inhibitor testing and the FVIII:C pre-dose assessment are taken.

- f An unscheduled visit may be required to repeat inhibitor testing under this protocol in order to obtain a sample to confirm a positive inhibitor test result.
- g If ITI success is declared, a sample will be collected at the first visit in the tapering period and at the end of the tapering period. If partial success or failure is declared a sample will be collected at the end of treatment visit.
- h PK assessments for half-life determination are to be performed in patients with a low or negative titer after at least a 24-hour washout.
- i It is recommended that patient/caregivers enter dosing information immediately after an injection.

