## Serious adverse event (SAE)

An adverse event that meets one or more of the following criteria/outcomes is classified as serious:

- Results in death.
- Is life-threatening (i.e., at immediate risk of death).
- Requires in-patient hospitalization or prolongation of existing hospitalization.
- Results in persistent or significant disability/incapacity.
- Is a congenital anomaly/birth defect (i.e., in an offspring to the study patient).

Other medically important adverse events that may not result in death, be life threatening, or require hospitalization may be considered serious when, based upon appropriate medical

judgment, they may jeopardize the patient or may require medical or surgical intervention to prevent one of the outcomes listed above. Examples of such events are intensive treatment in an emergency room or at home for allergic bronchospasm, blood dyscrasias or convulsions that do not result in hospitalization or development of dependency or abuse.

In this study, the following events are considered medically important and must be reported as SAEs:

- Development of a confirmed positive inhibitor (>0.6 BU) during the tapering or follow-up periods
- A patient develops a Grade 2 or greater allergic reaction in association with administration of rFVIIIFc defined as follows using the Recommendations for Grading of Acute and Subacute Toxic Effects on the WHO scale [[WHO Handbook 1979](#)] [40]:
  - Grade 2: bronchospasm; no parenteral therapy needed
  - Grade 3: bronchospasm; parenteral therapy required
  - Grade 4: anaphylaxis

Allergic reactions, including anaphylaxis, have been reported with FVIII products. The patients/caregivers should be informed of early symptoms and signs of hypersensitivity reactions, including difficulty breathing, chest tightness, swelling of the face, rash, or hives. If such an event occurs while the subject is at home, the patients/caregivers should be instructed to seek immediate medical care for the subject.

- A patient develops a vascular thrombotic event, with the exception of IV injection site thrombophlebitis

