**PAREXEL International**  
**Statistical Analysis Plan**

#### **6.3.13.5 Consumption**

The total study drug consumption as well as the total consumption of bypassing agents will be calculated for each patient by period and listed using the respective period analysis sets. Consumption will also be summarized by period (in the standard absolute dose and dose/kg for the respective product) using the ITIFAS. The consumption for 'other' (per eCRF) bypassing agents will only be summarized, if at least 3 subjects took the specific product.

An additional listing will show the consumption of rFVIIIFc, Novoseven® and FEIBA® in the ITI period.

For the ITI Period, the Tapering Period and the Follow-up Period annualized consumption (AC) will also be calculated and summarized:

$$AC = CP \frac{365.25}{\text{length of period in days}}$$

Here, CP is the total consumption of the period in that study.

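### By-period adverse event columns in SAP 6.3.15.1 carry no person-time and an unsettled denominator, so counts and percentages partly reflect how long, and in whom, each period was observed

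*SAP*

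**What the plan says.** On the display, SAP 6.3.15.1 states: "The overall summary and the summary of TEAEs by SOC and PT will display AEs by period using columns for the different periods". The other AE summaries are split into parts by period. The overall summary is specified as numbers; percentages come from the general rule in SAP 6.3.1 that qualitative variables get counts and percentages. Protocol 9.3.5.1 also asks for tabulations by period and across all periods. Neither section mentions patient-years or an event rate.

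On period length, Protocol 7.1 plans "a maximum 60 week ITI period, a 16 week tapering period and a 32 week follow-up period". Protocol 7.1.3 lets tapering be modified with approval, and if it is prolonged, Protocol 7.1.4 says "the follow-up period should be shortened accordingly but should not be less than 24 weeks".

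On time adjustment elsewhere, SAP 6.3.13.5 states: "For the ITI Period, the Tapering Period and the Follow-up Period annualized consumption (AC) will also be calculated and summarized". SAP 6.3.13.3, 6.3.13.4 and 6.3.13.6 to 6.3.13.9 do the same for bleeds, missed days and hospitalizations. SAP 6.3.14 summarizes duration of exposure and exposure days, but specifies neither a split by period nor a link to the AE tables.

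On the denominator, SAP 6.3.15 and the titles of the 14.3.1 tables use ITIFAS for all safety variables. SAP 6.2.2 and Protocol 9.2 assign safety during tapering to TPFAS.

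On ascertainment, visits are every 2 to 4 weeks in ITI and tapering, then at weeks 28, 40 and 48 after ITI success. For safety laboratory tests, footnote d of Protocol Table 2 reads: "During the tapering period, samples should be drawn every 12th week for testing". After tapering they are repeated only at end of treatment. The study-specific SAE list in Protocol 7.5.6.1.1 includes "Development of a confirmed positive inhibitor (>0.6 BU) during the tapering or follow-up periods", with no counterpart in ITI.

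**The concern.** Describing safety and tolerability is a secondary objective. In a single-arm study with no tests and no confidence intervals, the tables are the safety analysis. Columns placed side by side will be read across. If they cover different lengths of time, a difference between them may mean only that patients were watched for longer in one than in another. Without patient-years, the reader of the table cannot tell how much of a difference is time, or even which way it runs.

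The denominator adds to this. Only ITI successes reach the later periods, so dividing by all dosed patients counts people who were never at risk there. Hospitalizations show the gap most plainly: they are also captured as SAEs, so the same event is time-adjusted in the pharmacoeconomic table and unadjusted in the SAE table.

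**Working it through.** **Inputs.** Period lengths are from Protocol 7.1 and 7.1.4, the 20 dosed patients from the Protocol synopsis, and the analysis sets from SAP 6.2.2 and 6.3.15. The documents give no AE rate, so a range is assumed and held constant across periods. The number entering tapering and the realized ITI times are also assumed.

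**The plan's own durations.** The maximum is built from "6 weeks of screening + 60 weeks of treatment +16 weeks of tapering + 32 weeks of follow-up" plus 2 weeks of safety follow-up: 6 + 60 + 16 + 32 + 2 = 116 weeks, as stated. The minimum is "4 weeks of screening + 36 weeks of ITI treatment + an additional 2 weeks for safety follow-up": 4 + 36 + 2 = 42 weeks, as stated. So 60 weeks of ITI is a ceiling, and an early failure contributes about 36. At full length the ratios are 60/16 = 3.75, 60/32 = 1.88 and 32/16 = 2.0.

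**Duration alone.** With rate r per patient-year and w weeks (365.25/7 = 52.18 weeks per year), the chance of at least one AE is P = 1 − exp(−r × w / 52.18). For r = 1 and w = 60: 1 − exp(−1.150) = 68.3%.

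| Assumed r per year | ITI 60 wk | Tapering 16 wk | Follow-up 32 wk |
|---|---|---|---|
| 0.25 | 25.0% | 7.4% | 14.2% |
| 0.5 | 43.7% | 14.2% | 26.4% |
| 1 | 68.3% | 26.4% | 45.8% |
| 2 | 90.0% | 45.8% | 70.7% |
| 4 | 99.0% | 70.7% | 91.4% |

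These are percentages of patients who entered the period. Expected event counts per patient at r = 1 are 1.15, 0.31 and 0.61.

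**Varying the lengths, at r = 1.**
- ITI of 36 weeks: 49.8%.
- ITI of 12 weeks (an early success): 20.5%, which is below the 26.4% for tapering.
- An assumed mix of 7 successes at week 30, 5 failures at week 36 and 8 patients at week 60: 55.1%.
- Tapering prolonged to 24 weeks and follow-up cut to 24: 36.9% in both, so that contrast disappears.

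**Denominator, at r = 1.** Suppose 7 of 20 enter tapering and all 7 complete both later periods. Patients with an AE: 7 × 0.264 = 1.85 in tapering and 7 × 0.458 = 3.21 in follow-up. On period entrants this is 26.4% and 45.8%; on ITIFAS, 1.85/20 = 9.2% and 3.21/20 = 16.0%.

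**Pooled rate in the same example.** Patient-years are (7×30 + 5×36 + 8×60)/52.18 = 870/52.18 = 16.7 in ITI, 7×16/52.18 = 2.1 in tapering and 7×32/52.18 = 4.3 in follow-up. Expected events equal those figures at r = 1, so total events over total patient-years is 1.0 in every column. The 2.1 patient-years also show how little information tapering carries.

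**Per-patient formula.** The SAP's 365.25/length factor gives each patient an individual rate and weights all patients equally. One event in a 14-day stay would score 365.25/14 = 26.1 per year. It is not a pooled rate and is unstable for short stays.

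**The case against.** The strongest reply is that no comparison between periods is planned. The objective is to describe safety, the protocol itself asks for tabulation by period, and every AE is listed with dates, so in about 20 patients person-time could be worked out from the listings. That stands, and it limits the priority. It does not make the table interpretable as printed.

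Several stronger readings are tempting, and the documents do not support them:
- *AE percentages must fall when the dose is tapered.* The 68/26/46% pattern needs full-length ITI and a period-entrant denominator. A short ITI reverses the first contrast, and a 24/24-week split removes the second.
- *The SAP annualizes other endpoints so that periods can be compared.* The only reason given, in Protocol 9.3.4.4 for bleeding, is differing follow-up between patients.
- *The inhibitor rule hides an inflated SAE count.* A positive inhibitor is an entry criterion, so it could not be a new event at the start of ITI. Relapse is recorded as an SAE under its own term and is also tabulated separately.
- *Sparse follow-up visits leave time uncovered.* The AE question refers to all time since treatment began, and physical examination continues at each follow-up visit. Detection may be weaker, but no interval is left out.
- *A rate would isolate the drug effect.* It would not, because the later columns contain only ITI successes.

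**Conclusion.** The point holds as an interpretability gap. AE columns for periods of different and variable length have no person-time measure, and SAP 6.3.15 conflicts with SAP 6.2.2 and Protocol 9.2 on the denominator for tapering. At an assumed constant 1 AE per patient-year, full-length periods alone give about 68%, 26% and 46% of entrants. The size depends on the assumed rate, and both size and direction depend on realized ITI time. The denominator choice is comparably large: 26% against 9% in tapering and 46% against 16% in follow-up, if 7 of 20 enter. Priority is low to moderate: no test is planned, the primary endpoint is unaffected and the repair is cheap.

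**What to change.** In SAP 6.3.15.1 and Tables 14.3.1.1 and 14.3.1.2:

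1. Use the patients who entered each period as that column's denominator, print that number in the column head, and reconcile SAP 6.3.15 with SAP 6.2.2 and Protocol 9.2.
2. Add two rows per period: total patient-years observed, and the pooled rate (total events divided by total patient-years). Do not use the per-patient 365.25/length formula. State to which period the days up to the safety follow-up contact belong.
3. Footnote that visits and safety laboratory tests are less frequent in follow-up, that a confirmed positive inhibitor is an SAE only in tapering and follow-up, and that the later columns contain only ITI successes, so the rates do not isolate a drug or dose effect.
4. Optionally, add an SAE row that excludes inhibitor events.

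The cost is SAP wording and a few table rows, with no new data. If the database is already locked, SAP Addendum is the route the SAP provides. The downside is imprecise rates in the short tapering period: about 2 patient-years in the example above.

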Test product; dose and mode of administration:	In Europe and Canada, rFVIIIFc will be supplied as rFVIIIFc powder and solvent for solution for intravenous injection in different vial strengths. The manufacturing of drug substance and drug product for the clinical study will not differ from the manufacturing of commercial available ELOCTA®. Drug product will be packaged and labeled for clinical trial use. In USA, commercial available ELOCTATE® in different vial strengths, with additional labeling for clinical trial use, will be used as rFVIIIFc supply. Dose ITI period: 200 IU/kg/day which may be given as once daily doses, or divided in two doses per day. Dose tapering period: The dose and regimen will be adjusted by the investigator in accordance with local practice and investigator judgment. Dose follow-up period: Prophylactic dose decided by the investigator according to the label and clinical response of the patient.
Reference product; dose and mode of administration:	Not Applicable
Duration of treatment(s):	The maximum individual patient study duration is expected to be approximately 116 weeks, i.e., 6 weeks of screening + 60 weeks of treatment + 16 weeks of tapering + 32 weeks of follow-up + 2 weeks of safety follow-up.
Statistical methods:	Descriptive statistics will be used to summarize the outcomes in the study and no inferential statistics will be performed. Time to ITI success will be analyzed using Kaplan-Maier method. The proportion of patients achieving ITI success and partial ITI success will be calculated. The proportion of patients relapsing after achieving successful tolerance will be calculated. The number of bleeds for the ITI period will be summarized descriptively. For each of the tapering and follow-up periods the annualized bleeding rate will be calculated and summarized descriptively. Safety data will be presented descriptively across the entire study as

well as by each period. Consumption will be calculated for the entire study as well as for each of the periods separately.

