### **9.3.4 Analysis related to secondary objective**

#### **9.3.4.1 Time to ITI success**

Time to ITI success will be analyzed descriptively using Kaplan-Meier estimates including median, 25th and 75th quartile. A Kaplan-Meier plot will be generated. Patients not achieving ITI success during the up to 60 weeks ITI period will be censored at the last observed time for this analysis. The ITIFAS analysis set will be used for this analysis.

Time to ITI success will also be summarized descriptively for the patients achieving ITI success.

Time to confirmed negative titer will be analyzed in the similar way.

Time to confirmed Incremental recovery >66% of the expected IR will be analyzed similarly as well on the subset of patients who reached confirmed negative titer.

For the subset of patients who were classified as partial success at the end of the ITI period, the time to fulfillment of the criteria for partial success will also be analyzed descriptively.

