**9.3.5            Analysis of safety and tolerability data****9.3.5.1          Adverse events**

Reported adverse events during the study will be coded using MedDRA. The number of patients with any adverse events occurring after first dose of rFVIIIFc will be summarized in frequency tables, system organ class, preferred term, and maximum severity. Listings of adverse-event subgroups such as serious adverse events and adverse events leading to discontinuation will be also presented.

Separate tabulations of adverse events, serious adverse events and non-serious adverse events will be made for ITI period, including tapering period and follow-up period as well as across all periods.

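### The SAP lays out every adverse event summary by period and names no all-periods total, although the protocol requires tabulation across all periods as well.

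*SAP*

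**What the plan says.** **Adverse events, protocol.** The synopsis (Statistical methods) states: "Safety data will be presented descriptively across the entire study", and adds a presentation by period. Section 9.3.5.1 says that separate tabulations of AEs, SAEs and non-serious AEs "will be made for ITI period, including tapering period and follow-up period as well as across all periods". It also has patients summarised by SOC, preferred term and maximum severity, for events after the first dose.

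**Adverse events, SAP.** Section 6.3.15.1 shows the overall summary and TEAEs by SOC and PT in one column per period. For everything else: "All other AE summaries will also be by period but will be split into multiple parts by period". The titles of Tables 14.3.1.1 to 14.3.1.6 all refer to period. Pre-treatment SAEs are to appear as a period of their own.

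**Consumption.** The synopsis says: "Consumption will be calculated for the entire study as well as for each of the periods separately". Protocol 9.3.4.5 names only the ITI, tapering and follow-up periods. SAP 6.3.13.5 says that consumption "will be calculated for each patient by period" and summarises it the same way; Tables 14.2.3.1 and 14.2.3.2 are titled by period.

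**Time to partial success.** For patients classified as partial successes, protocol 9.3.4.1 says that "the time to fulfillment of the criteria for partial success will also be analyzed descriptively". SAP 6.3.13.1 does not mention this and the SAP's table list has no such table, yet the appendix title in SAP section 11 still includes partial success.

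**The concern.** Describing safety and tolerability is a stated secondary objective, and its most basic result is how many of the treated patients ever had a given event on rFVIIIFc. Only ITI successes go on to tapering and follow-up, and those patients stay in the ITI column too. A patient with the same preferred term in ITI and again in tapering is therefore counted once under each period. Event counts can be added across periods; patient counts cannot. The SAP describes itself as outlining the programming specifications for the tables, so tables programmed as written would lack the all-periods result that the protocol promises.

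Severity is affected in the same way. A patient whose event is mild in one period and severe in another needs a single maximum-severity classification over the study. The SAP's severity tables give no per-patient rule for this.

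**Working it through.** The plan states no figure to reproduce: there is no formal sample size calculation, and the documents contain no adverse event counts. The check is a comparison of texts, followed by bounds.

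**Comparison**

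| Item | Protocol | SAP |
|---|---|---|
| AEs, SAEs, non-serious AEs | By period and across all periods (synopsis; 9.3.5.1) | Period columns or period parts (6.3.15.1; Tables 14.3.1.1–6) |
| Consumption | Entire study and by period (synopsis); periods only (9.3.4.5) | By period (6.3.13.5; Tables 14.2.3.1–2) |
| Time to partial success | Descriptive summary (9.3.4.1) | Absent from 6.3.13.1 and the table list; named in section 11 |

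In SAP 6.3.15.1 the word overall qualifies the type of summary and the kind of event (TEAEs irrespective of seriousness). It does not refer to pooling over periods.

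**Bounds on patients ever affected**

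Let *N* = 20 (planned patients, protocol 7.1) and let *s* be the number entering tapering and follow-up. Let *a*, *b* and *c* be the patients with the event in ITI, tapering and follow-up, where *b* and *c* cannot exceed *s*.

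- Lower bound: *L* = max(*a*, *b*, *c*), when the same patients recur.
- Upper bound: *U* = min(*a* + *b* + *c*, *a* + *s*, *N*), when recurrence is as small as possible.

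All counts below are assumptions.

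| *a* / *b* / *c* | *s* | *L* | *U* | Share of 20 |
|---|---|---|---|---|
| 8 / 3 / 0 | 3 or more | max(8, 3, 0) = 8 | 8 + 3 = 11 | 40%–55% |
| 5 / 2 / 2 | 4, 8, 12 or 16 | 5 | 5 + 2 + 2 = 9 | 25%–45% |
| 10 / 4 / 3 | 4 | 10 | 10 + 4 = 14 | 50%–70% |
| 10 / 4 / 3 | 8, 12 or 16 | 10 | 10 + 4 + 3 = 17 | 50%–85% |
| 12 / 4 / 3 | 4 | 12 | 12 + 4 = 16 | 60%–80% |
| 12 / 4 / 3 | 8, 12 or 16 | 12 | 12 + 4 + 3 = 19 | 60%–95% |

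When *a* is the largest count, the width *U* − *L* is at most *s*. The ambiguity is therefore capped by the number of ITI successes. An all-periods column reduces each range to one number.

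**Consumption**

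Totals in IU add within a patient, and on a common denominator means add across periods. Medians do not. Take a toy set of ten patients with ITI amounts 1 to 10 and later amounts 9, 0, 0, 0, 0, 8, 0, 0, 0, 7. The period medians sum to 5.5 + 0 = 5.5, while the median of the patient totals is 7.5. The mean is 7.9 either way.

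**The case against.** **The SAP never says that totals are excluded.** A reader might infer a deliberate decision to drop them. The documents do not support that: the SAP is silent, records no such decision, and the table shells are not available. A total could still be added at shell stage. What stands is that the SAP fixes the layout of every AE summary, names the one extra part it wants (pre-treatment SAEs), and nowhere names a total.

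**The data are not lost.** A reader might infer that overall incidence is unrecoverable. It is not. Listing 16.2.10.1 gives all AEs, and Listings 14.3.2.2 and 14.3.2.3 give SAEs and AEs leading to discontinuation. A hand count in about 20 patients is feasible. This limits the point to the tables, but a listing is not the tabulation that the protocol promised.

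**The ambiguity may be small.** SAP 6.3.13.1 considers it likely that the success rate will be too low to estimate the median time to success. Few successes mean few patients who can recur, and the cap of *s* confirms this. The objection stands as to size.

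**The severity tables.** It is tempting to call the split into serious and non-serious tables a departure. Protocol 9.3.5.1 itself orders separate tabulations, and the SAP's overall summary includes severity of AEs without that split. Protocol 7.5.6.1.3 also defines the recorded severity of an event as its maximum intensity. Only the rule for a patient with several events of one preferred term is unstated.

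**Consumption is a weaker case.** The entire-study promise is in the synopsis alone; SAP 6.3.13.5 matches protocol 9.3.4.5. There is no double counting, because consumption adds within a patient, and Listing 16.2.9.1 covers rFVIIIFc consumption during the study.

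**Conclusion.** The point holds for adverse events. The protocol requires all-periods tabulations in two places, and the SAP specifies by-period layouts with no total and no recorded departure. Tables programmed as specified would only bound the number of patients ever affected: 8 to 11 of 20 in the assumed 8 and 3 example, and wider or narrower with other counts and with the number of ITI successes. These ranges rest on the planned 20 patients and on assumed counts; they are not forecasts.

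The periods themselves are sequential, so the difficulty is recurring patients and not overlapping time. The study is descriptive, and no primary or efficacy result changes.

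Two secondary points also stand. The descriptive time-to-partial-success summary is missing from SAP 6.3.13.1; its survival in the section 11 title suggests an oversight and not a decision. On entire-study consumption, the protocol's synopsis and body disagree with each other, and the SAP follows the body.

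**What to change.** - **Adverse events.** Add an 'All periods' treatment-emergent column to Tables 14.3.1.1 and 14.3.1.2, and a corresponding part to Tables 14.3.1.3 to 14.3.1.6. Count each ITIFAS patient once per SOC and PT, at maximum severity in the severity tables as protocol 9.3.5.1 states. Keep pre-treatment SAEs separate. State this in SAP 6.3.15.1.
- **Time to partial success.** Restore the descriptive summary in SAP 6.3.13.1 and add it to the table list.
- **Consumption.** Reconcile the synopsis with protocol 9.3.4.5 and SAP 6.3.13.5, for example by adding one entire-study row, summed per patient, to Tables 14.2.3.1 and 14.2.3.2.

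If any of these is not wanted, record the departure from the protocol with its reason. After database lock, the SAP's own route for changes is an addendum.

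The cost is one column in two tables, one part in four, one row in two and one short summary. No new data are needed.
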